### 4.2.2 Secondary outcomes

#### Breastfeeding rates

- d)** Proportion of exclusively breastfeeding infants vs. partially breastfeeding in each group at 24 hours, 1, 2, 4, 6, and 8 weeks post-partum, will be analyzed with mixed effects logistic regression (with restricted maximum likelihood) and visualized by a bar plot.
- e)** Proportion of any breastfeeding infants vs. formula in each group at 24 hours, 1, 2, 4, 6, and 8 weeks post-partum will be analyzed with mixed effects logistic regression (with restricted maximum likelihood) and visualized by a bar plot.

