### 2.2 Adherence to the intervention

We consider all participants who answer weekly questionnaires until 8 weeks post-partum as full completers. E.g. if participants try to follow the intervention as well as possible, but do not stimulate the breast the recommended fourteen times a week, we will still consider them as completers of the study, if they have stayed in the study during the intervention and until eight weeks after birth. However, we will differentiate between study completion and intervention completion. Intervention completion is defined as participants who follow the intervention as well as possible until birth but do not answer all eight questionnaires. These participants will be included in the analysis for gestational age at birth, but will only be included in the breastfeeding analysis as long as they have answered the weekly questions. If participants do not want to perform stimulation anymore, we consider this as a withdrawal of consent. If participants are not adherent to the randomized group, e.g. they start to stimulate antenatal even though they are in the control group, we consider them as excluded from the study.

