### 2.3 Intention to treat (ITT) and per protocol (PP) analysis

We will apply a modified ITT principle, considering only the participants who started the antenatal stimulation and/or participated in the breastfeeding consultation and as the ITT population. Participants who drop out before the breastfeeding consultation for any reason will not be included in any of our analyses. We consider PP as all of the participants who completed questionnaires until 8 weeks post-partum, no matter how well they complied with the intervention. We will apply ITT and PP analysis to our primary and secondary outcomes.

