## 3. Study design

### 3.1 Randomization

All participants will be randomized 1:1 into one of two arms: Group A aBME from week 34+0 or Group B no aBME. Randomization in this pilot trial will not be blinded to participants or investigators performing the data analysis due to the intervention type.

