#### Clinical features on infants

- Gestational age at birth (weeks+days)
- Gender (boy/girl)
- Birthweight (g)
- Birth length (cm)
- Head circumference (cm)
- APGAR score at 1 min (0-10)

- APGAR score at 5 min (0-10)
- Enteral Nutrition PP if hospitalized
- Way of feeding PP if hospitalized
- IV-solutions PP if hospitalized

Breastfeeding rates up to 8 weeks PP (both groups, weekly questionnaires):

- Feeding the first 24 hours (Did your child get anything other than your milk, yes/no)
- Are you breastfeeding (yes/no)
- If yes (Partially or exclusively breastfeeding)

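### From week 1, analysis d) covers only mothers still breastfeeding, so no planned model compares exclusive feeding between arms among all responding women at weeks 1 to 8

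*SAP*

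**What the plan says.** SAP 4.2.2 plans two breastfeeding comparisons. Analysis d) is the "Proportion of exclusively breastfeeding infants vs. partially breastfeeding in each group". Analysis e) is the "Proportion of any breastfeeding infants vs. formula in each group at 24 hours, 1, 2, 4, 6, and 8 weeks post-partum". Both use the same time points, and both are to be "analyzed with mixed effects logistic regression (with restricted maximum likelihood"), so each has a binary outcome.

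The data items are listed at the end of SAP 4.1, under the clinical features of the infants. Each week the mother is asked whether she is breastfeeding. The second step is conditional: "If yes (Partially or exclusively breastfeeding"). For the first 24 hours there is a single item, not conditional on breastfeeding: "Did your child get anything other than your milk, yes/no".

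Other provisions bear on who is counted:

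- SAP 2.2 says that women who complete the intervention but not every questionnaire "will only be included in the breastfeeding analysis as long as they have answered the weekly questions".
- SAP 2.3 says "We will apply ITT and PP analysis to our primary and secondary outcomes".
- SAP 4.5 uses available data without imputation.
- Secondary outcome 4 in the protocol names the same exclusive against partial contrast as d), at weeks 1 to 8. Secondary outcome 3 refers to breastfeeding rates without saying whether any or exclusive feeding is meant.

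**The concern.** Whether a mother is still breastfeeding at week 4 is itself an outcome, which may depend on the arm; e) treats it as one. If d) is restricted to those who are, it compares subsets selected after randomisation, not the randomised groups.

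Inclusion criterion 5 requires every woman to plan exclusive breastfeeding. Partial feeding and stopping are therefore both departures from that plan, but d) counts only the first. Suppose expression keeps in the partial group some women who would otherwise have stopped. Then d) read alone moves against expression, although no fewer women feed exclusively. It can also show no difference where the exclusive rate among all women does differ.

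The SAP does not state d)'s denominator. If it stays open, it will be settled during analysis by people who know the allocation: the trial "will not be blinded to participants or investigators performing the data analysis".

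**Working it through.** **What the text implies.** A logistic model of exclusive against partial needs one of those two values. From week 1 they come only from the conditional item. A mother who answers no to breastfeeding has neither value, and no rule in the SAP assigns her one. She still contributes the earlier weeks in which she was breastfeeding, and she is counted in e) as not breastfed. Since e) pools exclusive with partial, neither model gives exclusive feeding among all who answered at weeks 1 to 8. The 24-hour item goes to everyone and can classify all responders as exclusive or not at that one time point.

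**Inputs.** The protocol plans 30 women per arm. The documents give no stopping or partial-feeding rates, so there is no stated figure to reproduce. All counts below are assumed, for one visit with all 30 women answering in each arm.

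**Formulas.** Write E, P and S for exclusive, partial and stopped, with A for antenatal expression and B for control.

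- Share on d)'s denominator: E/(E+P)
- Crude odds ratio on d)'s denominator: (E_A × P_B)/(P_A × E_B)
- Exclusive among all: E/30
- Any breastfeeding, as in e): (E+P)/30

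| A: E/P/S | B: E/P/S | d)'s denominator, A v B | Crude OR | Exclusive among all | e), any breastfeeding |
|---|---|---|---|---|---|
| 18/9/3 | 18/9/3 | 67% v 67% | 1.00 | 60% v 60% | 90% v 90% |
| 18/11/1 | 18/12/0 | 62% v 60% | 1.09 | 60% v 60% | 97% v 100% |
| 18/10/2 | 18/9/3 | 64% v 67% | 0.90 | 60% v 60% | 93% v 90% |
| 18/9/3 | 18/6/6 | 67% v 75% | 0.67 | 60% v 60% | 90% v 80% |
| 18/6/6 | 18/9/3 | 75% v 67% | 1.50 | 60% v 60% | 80% v 90% |
| 18/9/3 | 16/8/6 | 67% v 67% | 1.00 | 60% v 53% | 90% v 80% |

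Fourth row in full: 18/27 = 0.667 and 18/24 = 0.750; odds ratio (18 × 6)/(9 × 18) = 0.67; exclusive among all 18/30 = 0.60 in both arms. Fisher's exact test on 18/9 against 18/6 gives p = 0.55, so at this size the shift is in the estimate and not in significance.

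Last row: (18 × 8)/(9 × 16) = 1.00 on d)'s denominator, while among all women the odds ratio is (18 × 14)/(12 × 16) = 1.31.

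**How d) and e) fit together.** P(exclusive) = P(any) × P(exclusive given any). Fourth row: 0.90 × 0.667 = 0.60 and 0.80 × 0.75 = 0.60. Last row: 0.90 × 0.667 = 0.60 and 0.80 × 0.667 = 0.53. Read together, the two analyses recover the exclusive rate; no planned model tests it.

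**The 24-hour item.** A yes cannot separate partial from no breastfeeding, so the item alone cannot supply e) at 24 hours. In d) it makes the comparator not exclusive at 24 hours but partial later. The protocol's Background puts initiation in Denmark at 97% to 99.5%. If that applied here, 30 × 0.03 = 0.9 to 30 × 0.005 = 0.15 infants per arm would not be breastfed, so the effect on d) is small.

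**The estimator.** Restricted maximum likelihood belongs to the linear mixed model. For a logistic mixed model it is not a defined estimator unless a particular approximation is named, and the SAP names none.

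**The case against.** The best defence is that d) does what the protocol asks: secondary outcome 4 names exclusive against partial. That is true, and it is a reason to keep the contrast. It does not supply the missing comparison.

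A second defence is that d) and e) are complementary. This also stands. In both examples with 10% against 20% stopping, e) shows 90% against 80%, so differential stopping would not be hidden. The exclusive rate among all women can be derived from the data collected.

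A third is that the denominator is merely ambiguous. A proportion in each group can be read as a share of the group, SAP 2.2 and 2.3 point towards all responders, and partial may loosely mean not exclusive. But 2.2 and 2.3 govern who enters the analysis and give a mother who stopped no category in d). SAP 4.1 makes partial a subset of yes, and e) puts formula in a separate contrast.

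A reader might infer more than the documents support:

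- **That exclusive feeding among all women is compared nowhere.** The 24-hour item covers all responders, and d) includes that time point.
- **That mothers who stop are lost altogether.** They keep their earlier weeks in d) and remain in e).
- **That the odds ratios above are what d) would estimate.** They are crude single-visit ratios on assumed counts; the SAP specifies a repeated-measures model.
- **That e) has no possible data at 24 hours.** The protocol's Data collection section mentions medical records for feeding from birth and questions on breastfeeding initiation. What is missing is mostly a cross-reference.

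**Conclusion.** The point holds for weeks 1, 2, 4, 6 and 8. On the plain reading d) conditions on still breastfeeding, e) pools exclusive with partial, and no planned model compares exclusive feeding among all women who answered.

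The size is unknown because the documents give no stopping rates. In the assumed examples the crude odds ratio on d)'s denominator runs from 0.67 to 1.50 when exclusive feeding among all is 60% in both arms, and is 1.00 when it is 60% against 53%. These larger shifts need stopping to be twice as common in one arm. With equal stopping the effect is nil; with few stopping it is small (0.90 to 1.09).

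This is a secondary outcome in a 60-woman pilot. The step to a larger trial is tied to preterm birth, so the point does not touch that decision. It should be corrected because the correction needs no new data and settles the definition before unblinded analysts have to choose it. The estimator wording needs correcting in any case; the 24-hour source for e) is minor.

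**What to change.** In SAP 4.2.2:

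1. Add to d) a mixed effects logistic model of exclusive against not exclusive (partial or none), with all women who answered at that time point in the denominator. Name it as the main comparison of exclusive feeding. A no to the weekly breastfeeding question counts as not exclusive; the 24-hour item already fits this definition.
2. Keep the exclusive against partial contrast of protocol outcome 4. State that its denominator is mothers still breastfeeding, and that it is to be read together with e).
3. Replace restricted maximum likelihood with maximum likelihood for d) and e).
4. Name the source, among data already collected, that supplies e) at 24 hours.

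This changes SAP wording only, and the main change uses items already in the weekly questionnaire. The cost is one extra secondary analysis.

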Antenatal breastmilk expression from 34 weeks of gestation.

Safety in pregnancy and benefits for the newborn infant: protocol for a
pilot randomized study

The EXPRESSMOM Study

Background

The World Health organization (WHO) recommend exclusive breastfeeding to 6 month of age, and for up to 2 years of age along with introduction to solid foods (1). According to their data, only 38% of all children aged 0-6 months are exclusively breastfed. The 2025 goal for WHO is to increase the rate of exclusively breastfed infants aged 0-6 month to at least 50%. In Denmark, only 16.9% of infants are exclusively breastfed at 6 months, although between 97 – 99.5% initiate breastfeeding right after birth (2, 3).

Mother's own milk (MOM) is the best feeding option for all newborn infants, including those born preterm. Besides being a source of macronutrient nutrition, MOM is also a source of vitamins, minerals and bioactive components, such as growth factors, immunoglobulins, lactoferrin, antioxidants and cytokines. These bioactive components contribute, among others, to activate the immune system, mature the infant intestine and promote neurodevelopment (4). In addition, breastfeeding has benefits for both mother and infant. Breastfed children have a reduced risk for various diseases later in life e.g. cardiovascular and metabolic diseases and obesity (5-7). Furthermore, women who breastfeed seem to have a reduced risk for breast- and ovarian cancer, osteoporosis as well as diabetes later in life (7).

MOM is complex and changes throughout the lactation period and by that adapt to the current need of the infant (8). The first milk, colostrum, is very valuable and contains a high amount of fat, protein and bioactive components, important for the infant, compared to mature milk, which primarily content is carbohydrates. If MOM is not available right after preterm birth, the infant receives donor human milk (DHM) or infant formula (IF) depending on gestational age. Mothers who deliver preterm often have a delayed onset of lactation (9), and they do not produce enough MOM until several days after delivery. Therefore, the primary source for enteral feeding for the preterm infants the first days of life will be DHM. DHM is mature milk, and contains lower amounts of protein, fat and bioactive components.

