Randomized pilot study with 1:1 into one of two arms: Group A aBME from week 34+0 or Group B no aBME. Randomization in this pilot trial will not be blinded to participants or investigators performing the data analysis due to the intervention.

Participants/Population

Participants are nulliparous pregnant women from the island of Funen who plan to give birth at Odense University Hospital. We intend to include 60 pregnant women, 30 in each group. If recruitment rate is low, we will widen the inclusion criteria and also include multiparous women who do not breastfeed siblings.

Inclusion criteria:

1. Healthy nulliparous women with no major chronic or pregnancy related diseases

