2. BMI <27
3. Danish speaking
4. Singleton pregnancies
5. Planning to exclusively breastfeed their infants and deliver at Odense University Hospital (Odense and Svendborg)

Exclusion:

1. Suspected fetal intrauterine growth restriction or known major fetal anomaly
2. Women at risk of preterm birth with one of the following diagnoses: Placenta previa, premature preterm rupture of membranes (PPROM) or previous cervical conization
3. Women taking medications where breastfeeding is contraindicated
4. Women with prior breast surgery: Breast reductive surgery or breast implants

Ethical approval

Application for the Ethical Committee of Southern Denmark (project number: 86409) is done and the committee decided that no regional ethical approval is necessary in order to perform this study. The Research Ethics Committee of University of Southern Denmark has approved the study (Project ID: RECID281). All data collected will be entered and stored on a secure server in the Region of Southern Denmark, OPEN (www.open.rsyd.dk) and the project is approved by the Data Protection Agency at the Region of Southern Denmark. The study will be registered at clinicaltrials.gov.

Recruitment and information

[figure not shown]
Participants will be recruited using video and text announcing on social media and in outpatient/midwife clinics in the department of obstetrics. If the women are interested in participation, they click on a link and fill in an online document with contact information (telephone and email) and confirm that they comply with the inclusion criteria. After conforming their interest in participating, they receive written information about the trial (Appendix 1) through email. Following, primary investigator or others in the study group will contact them by telephone within 2-4 days to give oral information. Signed written consent will be obtained using E-Boks. Then randomization can be done and consultation in week 33 can be planned by the project-midwife by telephone.

Randomization

When the women have given informed written consent, they will be randomized to either group A (intervention) or B (control). Randomization will be done using a web-based randomization program (REDCap in OPEN). Baseline maternal characteristics, obstetric and neonatal will be obtained through medical records:

Maternal:	Neonatal:

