#### **4.6 Statistical software**

Statistical analysis will be carried out with Stata® statistical software

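### SAP 4.2.2 d) and e) name an estimator (REML) that does not fit mixed logistic regression, and once that is corrected the odds ratio could still be unstable with 30 women per arm

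*SAP*

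**What the plan says.** SAP 4.2.2 (Breastfeeding rates) defines two repeated binary outcomes. Item d) is the "Proportion of exclusively breastfeeding infants vs. partially breastfeeding in each group" and item e) the "Proportion of any breastfeeding infants vs. formula in each group". Both are taken "at 24 hours, 1, 2, 4, 6, and 8 weeks post-partum". For each, the SAP says that the proportion "will be analyzed with mixed effects logistic regression (with restricted maximum likelihood"), with a bar plot. It gives no fixed effects, random effects, coding of time, arm-by-time term, effect measure, or rule for non-convergence or empty cells.

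SAP 4.6 adds only this: "Statistical analysis will be carried out with Stata® statistical software". No command or version is named.

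Three further facts bear on the point:
- Sample size (Protocol, Participants/Population): "We intend to include 60 pregnant women, 30 in each group".
- Early rates (Protocol, Background): between 97% and 99.5% of Danish mothers "initiate breastfeeding right after birth".
- Selection (Protocol, inclusion criterion 5): "Planning to exclusively breastfeed their infants" is a condition of entry.

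**The concern.** REML is defined for the linear mixed model. Stata's standard mixed-effects logistic commands maximise the likelihood by numerical integration and have no REML option. This is general knowledge of methods and software, not something the documents state. The analyst must therefore depart from the SAP at the first step.

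Switching to maximum likelihood does not settle the matter. A random-intercept logistic model estimates a conditional odds ratio, and two features of these data can make it unusable:

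- **Near one-way stopping, d) and e).** If every woman's answers are a run of yes followed by a run of no, a steeper curve always fits better. Scaling up the coefficients and the random-intercept SD together keeps raising the likelihood, and there is no finite maximum.
- **Empty cells, e) only.** If every woman in one arm is breastfeeding at a time point, an odds ratio specific to that time point is infinite, or undefined if both arms are full.

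At stake is the only specified between-arm analysis of Protocol secondary outcomes 3 and 4. The Protocol's general statistics section covers comparisons of means and rank or permutation tests, so it offers no fallback for repeated yes/no data. The analysts are not blinded (Protocol, Trial design; SAP 3.1), so a replacement would be chosen with the arms in view.

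**Working it through.** The documents state no figure for this model, so there is none to reproduce.

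**1. Full cells, outcome e).** Inputs: 30 per arm (Protocol) and a true rate p, equal in both arms. P(one arm is 30/30) = p^30, and P(at least one arm) = 1 − (1 − p^30)².

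| p | p^30 | at least one arm 30/30 |
|---|---|---|
| 0.995 | 0.860 | 0.98 |
| 0.98 | 0.545 | 0.79 |
| 0.97 | 0.401 | 0.64 |
| 0.95 | 0.215 | 0.38 |
| 0.90 | 0.042 | 0.08 |

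The range 97% to 99.5% comes from the Protocol's Background. The lower rows are assumptions, because the documents give no rates for weeks 1 to 8.

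**2. One-way stopping, constructed data.** Assumptions: no woman restarts; every woman without the outcome counts as a no; weeks 1, 2, 4, 6 and 8. The model has categorical week, an arm main effect and a normal random intercept, fitted by maximum likelihood at fixed values of the random-intercept SD.

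Counts of yes out of 30 for e): control 29, 28, 27, 25, 24; expression arm 30, 29, 29, 28, 27. For d): control 25, 23, 21, 19, 18; expression arm 26, 25, 24, 22, 22.

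| SD | e) log-likelihood | e) conditional OR | e) week-8 standardised difference | d) log-likelihood | d) conditional OR | d) week-8 standardised difference |
|---|---|---|---|---|---|---|
| 1 | −61.66 | 2.94 | 0.112 | −122.85 | 1.84 | 0.112 |
| 10 | −39.28 | 139 | 0.110 | −69.39 | 24.7 | 0.115 |
| 20 | −38.48 | 14,400 | 0.109 | −66.73 | 471 | 0.111 |
| 40 | −38.34 | 1.79 × 10^8 | 0.108 | −65.95 | 1.78 × 10^5 | 0.109 |

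The log-likelihood rises at every step while the odds ratio runs away. This happens for d) too, which has no full cell. The risk difference standardised from the same fits hardly moves.

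**3. Simulation, 30 per arm, SD capped at 40.** The rates are assumptions: any breastfeeding falling from 98% to 80% v 90%, or to 85% in both arms; exclusive breastfeeding falling from 85% to 60% v 75%. *Extreme* means an odds ratio above 100 or below 0.01.

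- Permanent stopping: the SD reached the cap in 98% to 100% of data sets, and 78% to 92% were extreme.
- 1% of answers flipped at random: 30% extreme for d), 33% for e).
- 2% flipped: 13% extreme for d), 3% to 7% for e).
- 5% and 10% flipped (d only): none extreme; median SD 3.9 and 2.2; median absolute log odds ratio 1.04 and 0.78.

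**4. The 24-hour point, d).** SAP 4.1 asks whether the child received anything besides the mother's milk in the first 24 hours. A child supplemented on day 1 and then exclusively breastfed is a reversal. Six time points were simulated with exclusive feeding falling from 85% to 60% v 90% to 75%, permanent stopping from week 1, and assumed 24-hour supplementation of 10%, 20% or 30%. The SD reached the cap in 0 of 90 data sets, median odds ratios were 3.8, 3.4 and 2.8, and 1 of 90 was extreme.

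**5. The alternative.** Newcombe 95% intervals for the difference, on illustrative counts:
- 30/30 v 28/30: 6.7 points (−5.7 to 21.3), where the sample odds ratio is infinite.
- 27/30 v 24/30: 10.0 points (−8.8 to 28.5), where it is 2.25.

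**The case against.** The strongest reply is that the only demonstrable error is one parenthesis. Without it, d) and e) describe an ordinary model that Stata fits, and the rest depends on conditions the documents do not state. Much of this stands:

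- **Permanent stopping is an assumption.** The weekly items in SAP 4.1 can record reversals, and steps 3 and 4 show that modest numbers of them give d) finite, moderate estimates.
- **The 97% to 99.5% rate is limited.** It describes initiation of any breastfeeding in the general population. It says nothing about exclusive versus partial feeding, and the full-cell probability falls quickly below 97%.
- **An infinite term needs a week-specific odds ratio**, and the SAP states no arm-by-time term.
- **The SAP names no odds ratio.** Its targets are proportions by arm, to be shown in bar plots, and a standardised difference from the same model is stable.

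A reader might also compare a large conditional odds ratio with the week-8 odds ratio computed from the arm proportions and call the gap bias. That is not supported: the two are different quantities, and the conditional one is legitimately further from 1.

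What does not stand is that deleting the label suffices. The model terms, effect measure and fallback would still be missing, and the most readily reported output, the conditional odds ratio, is the fragile one.

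**Conclusion.** The estimator named for d) and e) is wrong for the model, and that part cannot be executed as written. With maximum likelihood in its place, the conditional odds ratio is at high risk of instability at 30 per arm. It diverges in both outcomes if stopping is almost one-way. For e), a week-specific odds ratio is infinite or undefined with probability 64% to 98% at early rates of 97% to 99.5%, falling to 38% at 95% and 8% at 90%.

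A reader might infer that the model cannot be fitted at all, or that it must return an absurd result in place of a difference in proportions. The documents support neither: they leave the terms and effect measure open, and they do not say that stopping is permanent.

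The severity is moderate. These are secondary outcomes of a 60-woman pilot, and progression to the larger trial (Protocol, Sample Size) turns on preterm birth, not on breastfeeding.

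**What to change.** In SAP 4.2.2 d) and e):

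1. Delete the REML wording.
2. At each time point, report both proportions and their difference with a Newcombe 95% interval, as the main between-arm comparison.
3. If the mixed model is kept, specify maximum likelihood with adaptive quadrature, arm and time as main effects, and a random intercept per woman. Report the standardised (marginal) risk difference, not the conditional odds ratio. Name the per-time-point differences as the fallback if the model does not converge.

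The cost is SAP wording and simpler code, with no new data. The price is less efficient use of the repeated measures and several intervals per outcome.

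Two other summaries have limits. A population-averaged (GEE) model with arm-by-week terms on the logit scale meets the same full-cell problem: on the constructed e) data, the 30/30 cell gave a log odds ratio of 22.2. Any GEE summary should leave those terms out. It also generally needs stronger missing-data assumptions than a likelihood-based model, which matters because SAP 4.5 rules out imputation. A log-rank comparison of time to stopping ignores women who restart.
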